4. **PHASE 2 (day 5 to 12): INFORMED CONSENT #2:** Study patients judged clinically suitable, by the study surgeon, for early ileostomy closure, will be asked to review and sign informed consent #2 for SLIRPS trial participation. Oral and written description of the trial will be presented to subjects who satisfy the inclusion criteria and initial and secondary exclusion criteria and express interest in participation. Consent will be obtained by the study surgeon or assistant at each site. After informed consent is obtained, the patient will be registered into the trial.
5. **PHASE 2 (day 5 to 12): IPAA Radiological Assessment** will be performed on **day 5-12** after IPAA on all study patients who are determined by the study surgeon to be clinically suitable for early ileostomy closure and who have provided informed consent (#1 and #2) to participate in the trial.
 - a. Radiologic assessment will be performed at day **5 to 12** after IPAA ostomy surgery. CT or fluoroscopic imaging of the IPAA with a water-soluble contrast medium will be performed to visualize the IPAA and determine the presence of radiologic leak. With either imaging modality, the enema contrast medium is instilled using a soft catheter.
 - b. **Subjects not radiologically suitable for early ileostomy reversal:** Study patients with a radiological leak from the IPAA will **not be randomized** to early or late closure. Details of the radiologic leak will be captured in CRF-4 (IPAA assessment). The patient will not be randomized to control or experimental trial arms. Treatment of these patients will follow the standards of care.
 - c. **Subjects radiologically suitable for early ileostomy reversal:** Study patients with no radiologic leak from the IPAA will be randomized to the control or experimental study arms. (CRF-4)
6. **PHASE 2 (day 5 to 12): RANDOMIZATION:** Immediately after IPAA radiologic assessment, study patients with no radiologic leak will be randomized to early (post-IPAA day 7 to 12) or late (post-IPAA \geq 8 weeks) ileostomy closure via the REDCap data collection system. The randomization scheme will be established by the study biostatistician. The randomization will be stratified by study site. Within each site, randomly

Timing of Ileostomy Closure after Ileal Pouch Surgery

selected block sizes of 2, 4, or 6 will be used so that the site investigators cannot predict beforehand the group to which the patient will be randomized.

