4 DESCRIPTION OF THE CLINICAL TRIAL SEQUENCE

Screening visit

Data to be recorded:

General parameters:

- Initials
- Age
- Gender
- ASA
- BMI
- Hemoglobin (g/dl)

Timing of Ileostomy Closure after Ileal Pouch Surgery

- Serum Albumin (g/dl)
- Active smoker (smoking within 1 month of IPAA)
- Bowel Preparation (choose: none, mechanical only, oral antibiotic only, mechanical AND oral antibiotic) Date of birth

Case history

Medication Use

- Anti TNF drug use within 8 weeks of IPAA surgery date
- Steroid use within 4 weeks of IPAA surgery date (excluding Budesonide)
- Vedolizumab drug use within 8 weeks of IPAA surgery date
- Other colitis drugs (e.g. methotrexate, azathioprine, 5-ASA) within 4 weeks of IPAA surgery date

Examinations

- Vital signs: blood pressure (mm Hg), heart rate (min^{-1}), weight (kg), calculation of BMI
- Physical examination: Routine preoperative examination
- Blood draw: blood hemoglobin, serum albumin, other blood tests at discretion of surgeon

Formal aspects:

Informed consent procedure

Verification of inclusion / exclusion criteria (eligibility check), as far as possible

PHASE 1, IPAA Surgery

IPAA surgery type

- Proctocolectomy with IPAA (2-stage procedure)
- Completion proctectomy with IPAA (3-stage procedure)

Indication for proctocolectomy or colectomy

- Colitis symptoms inadequately controlled by medical therapy or steroid-dependence
- Colorectal epithelial dysplasia

Timing of Ileostomy Closure after Ileal Pouch Surgery

Urgency of colectomy or proctocolectomy

- Urgent (colectomy or proctocolectomy performed on a hospitalized patient)
- Elective (colectomy or proctocolectomy performed on a patient who was not hospitalized on the day before surgery)

IPAA Surgery Details

- Duration of surgery (cut to close, minutes)
- Open removal of colon and rectum
- Laparoscopic proctocolectomy
- Laparoscopic colectomy with open proctectomy
- Hand assisted laparoscopic (HAL) proctocolectomy
- HAL colectomy colectomy with open proctectomy
- Robotic proctocolectomy
- Robotic colectomy with open proctectomy
- Lap, HAL, or Robotic proctocolctomy or colectomy with unplanned conversion to open surgery
- Trans-anal-trans-abdominal IPAA
- Stapled IPAA
- Sutured IPAA
- IPAA anastomotic leak test performed (yes/no)
- IPAA anastomotic leak test result: no leak, small leak, big leak
- Ileal pouch bleeding that required suture placement or other methods to stop bleeding
- IPAA tension (none, minimal, moderate)
- EBL

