10 STATISTICAL CONSIDERATIONS

Sample Size Calculation

The developers of the CCI consider a 10-point difference in their 0 to 100 morbidity scale to be clinically meaningful; it reflects a 1-grade difference in the established Clavien-Dindo classification of postoperative complications (Slankamenac, 2014; Clavien, 2009). They also report a standard deviation of the CCI of 20-22 in two surgical trials. Assuming 80% power and an $\alpha = 0.05$ level of significance, our trial would need about 63-76 patients per group, or a total of 126-152 patients to complete both phases of the trial. It is anticipated that up to 600 patients will be required for phase 1 due to the expected $\leq 75\%$ drop out of phase 1 patients who are not eligible for phase 2.

Statistical analyses

A Consort Diagram will be used to account for all patients screened for inclusion in the trial; those who were excluded and included and reasons for exclusion; those who were randomized; and those who were followed at each time point or who were lost to follow-up. The primary analysis will be by intention-to-treat, meaning that the patients will be analyzed by the group to which they were randomized. This means that patients randomized to the short interval closure group who have postoperative complications that delay closure will still be analyzed in the group to which they were randomized. Secondary analyses will be done per-protocol (analyzing patients who followed the protocol), and as-treated (analyzing patients by the treatment they actually received).

Patient baseline characteristics will be compared between the early and late closure groups using a chi-square test for categorical variables and a t-test for independent samples for normal continuous variables or a Wilcoxon two sample ranks test for non-normal continuous variables.

Complications will be reported using the Clavien-Dindo classification. Perioperative details in the two groups will be compared using the same methods as were used for comparing the patient baseline characteristics.

The primary analysis will be comparing Comprehensive Complication index and overall complication rates up to 6 months postoperatively between the two randomized groups using a generalized linear model with a log-link function with

Timing of Ileostomy Closure after Ileal Pouch Surgery

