group (short vs. long interval closure) and hospital as the independent variables. We will also include any patient baseline characteristics that remained unbalanced in spite of randomization. Secondary analyses will include a comparison of mean number of complications per patient using a zero-inflated Poisson model, and a comparison of severe complications (Clavien-Dindo Grade IIIa or higher) using the same methods as were used for the primary analysis. We will also compare the mean number of stoma related complications using a zero-inflated Poisson model. Since the quality of life scales are continuous variables measured over time, we will compare the early vs. late closure groups for these outcomes using linear mixed models.

DSMB interim analyses and early stopping rules for interim analyses

At their first meeting, the DSMB will decide how they wish to monitor the study. Typically, a DSMB will monitor all aspects of a study to ensure its scientific integrity, including patient screening and accrual, follow up, performance of individual centers, data acquisition and quality issues, adverse events, and outcomes. At the first meeting, we will also determine their desire in establishing formalized stopping rules. Any data presented by treatment group at the DSMB meeting will be blinded with regard to the identity of the comparison groups, and participating investigators (except for the study biostatistician) will not see any data broken down by treatment group during the course of the trial.

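### The primary CCI model admits covariates by chance imbalance under an unstated rule, so it stays open until data by group exist; the effect is modest and the remedy is wording

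*Combined protocol and SAP*

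**What the plan says.** Section 10 (Statistical analyses) specifies a log-link generalized linear model with "group (short vs. long interval closure) and hospital as the independent variables". The next sentence reads: "We will also include any patient baseline characteristics that remained unbalanced in spite of randomization". The Summary (Section 1) repeats it.

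The same section describes baseline testing: "Patient baseline characteristics will be compared between the early and late closure groups using a chi-square test for categorical variables", with t or Wilcoxon tests for continuous variables. It gives no significance level for these tests and does not connect them to covariate entry. The 0.05 in Section 10 belongs to the sample-size calculation.

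Operative data are treated apart: "Perioperative details in the two groups will be compared using the same methods as were used for comparing the patient baseline characteristics". Yet Section 3 places randomization after the pouch operation ("Immediately after IPAA radiologic assessment, study patients with no radiologic leak will be randomized"), so operation type, indication and urgency, listed under IPAA Surgery in Section 4, are also known before allocation.

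The covariate rule applies to "comparing Comprehensive Complication index and overall complication rates up to 6 months postoperatively" and, by reference, to "a comparison of severe complications (Clavien-Dindo Grade IIIa or higher) using the same methods as were used for the primary analysis".

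**The concern.** Two things are wrong with the rule. First, it is incomplete. It does not say how imbalance is judged, which variables are eligible, or whether the choice is made before outcomes by group are seen. Two analysts acting in good faith could fit different primary models to the same data.

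Second, even if completed, it selects on the wrong property. After proper randomization a baseline difference is chance. A covariate helps when it predicts the outcome, and observed imbalance says nothing about that. The rule therefore spends degrees of freedom on whatever happens to differ and leaves out prognostic variables that happen to be balanced.

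What is at stake is the reproducibility of the primary result and a little precision.

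**Working it through.** **Inputs from the documents.** Difference 10 CCI points, SD 20-22, 80% power, alpha 0.05, 126-152 patients (Section 10); 17-25 centers (Section 1); site-stratified blocks of 2, 4 or 6 (Sections 3 and 9); recorded items (Section 4).

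**Assumptions, not in the documents.** 126 patients in 21 hospitals of 6 (126/21 = 6). Imbalance is judged by p-value. There are 12 independent candidates: eight screening items (age, gender, ASA, BMI, hemoglobin, albumin, smoking, bowel preparation) and four medication items. Four variables are prognostic (BMI, albumin, steroid use, operation type), together explaining 5%, 10% or 15% of CCI variance; operation type is a candidate only when the set is widened to 15.

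**1. The plan's own figure.** n per group = 2 × [SD × (1.960 + 0.842)/10]². SD 20 gives 62.8, so 63; SD 22 gives 75.98, so 76. Totals of 126 and 152 match the plan (two-sided). The covariate rule does not affect this.

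**2. Entry by chance.** P(at least one of 12 flagged at 0.05) = 1 − 0.95^12 = 0.460. Cut-offs 0.05 and 0.10 give different sets when some p-value lies between them, an interval of width 0.05, so again 1 − 0.95^12 = 0.460 (simulated 0.45-0.46). Counting operation type, indication and urgency as baseline adds three candidates: 1 − 0.95^3 = 0.143 (simulated 0.147-0.149).

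**3. How often the verdict changes (true effect present).** The linear simulation used SD 20, effect 10 and 8,000 runs. The log-link simulation was quasi-Poisson with assumed control mean 24-25, SD 20-21, ratio 0.6, 37% zeros and 2,496 runs.

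| Readings compared | Linear | Log-link |
|---|---|---|
| 0.05 vs 0.10 | 2.7-3.1% | 2.2-3.4% |
| 12 vs 15 candidates at 0.05 | 1.1-1.4% | 0.9-1.1% |
| Both cut-offs with both candidate sets | 4.4-5.2% | 3.5-4.9% |
| None, 0.01, 0.05, 0.10, 0.20 | 9.0-10.5% | 9.3-9.9% |

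Between 0.05 and 0.10 the log-link ratio moves by a median of 0% and by 5-6% at the 90th percentile. A separate linear simulation (63 per group, no hospital terms, 15 candidates, three prognostic, variance explained 10/20/30%, 4,000 runs) compared none, 0.05, 0.10 and 0.20. It gave 10.1/11.7/13.7%.

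**4. Type I error.** The rule fixed at 0.05 rejects in 0.045-0.049 of null trials (linear) and 0.034-0.035 (log-link). Taking the smaller p of the 0.05 and 0.10 rules gives 0.050-0.053 (linear). Taking the best of none, 0.05, 0.10 and 0.20 gives 0.065/0.073/0.067 in the separate linear simulation; a further one with 21 sites of six and 12 candidates gave 0.064-0.069 for the best of four readings.

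**5. Power at 5/10/15% of variance explained.**

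| Model | Linear | Log-link |
|---|---|---|
| Group and hospital | 0.791/0.791/0.787 | 0.800/0.782/0.794 |
| Rule at 0.05 | 0.778/0.780/0.783 | 0.780/0.767/0.783 |
| Four fixed, all prognostic | 0.795/0.816/0.833 | 0.784/0.783/0.801 |
| Four fixed, two prognostic | 0.782/0.793/0.806 | 0.778/0.772/0.786 |
| Four fixed, none prognostic | 0.774/0.771/0.775 | 0.774/0.756/0.775 |

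Group and hospital alone beats the rule by 1.3/1.1/0.4 points (linear) and 2.0/1.5/1.1 (log-link). Four fully prognostic covariates beat group and hospital by 0.4/2.5/4.6 points in the linear model, but by −1.6/+0.1/+0.7 under the log link, where paired differences have a standard error of about 0.5 points.

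**The case against.** The strongest reply is that the gap is small and nearly closed by a sensible reading. Section 10 names the baseline tests, and 0.05 is the obvious level. Section 9 separates the screening and pre-IPAA forms from the operative form, which suggests that operative items are not baseline. Any single reading, applied mechanically, holds type I error, and neighbouring readings rarely change the verdict.

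Much of this stands. The form structure does make the candidate set less open than Section 4 alone suggests, and that ambiguity moves the verdict in only about 1% of trials. But no text ties the tests to covariate entry or sets their level, and even at a settled 0.05 the rule would still select on chance.

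Four stronger readings are tempting and are not supported:

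- A reader might infer that the rule inflates type I error. It does so only if the reading is chosen after seeing results.
- A reader might infer that the choice will be steered, because Section 8 gives the study biostatistician access to outcomes and excepts that role from the bar on data by group, and Section 9 assigns the analysis to the same role. The documents show only that nothing requires the choice to come first. Section 8 also masks the identity of the groups in data presented to the DSMB.
- A reader might infer that two co-primary endpoints are affected. Section 10 puts overall complication rates in the primary analysis, but Section 1 names CCI as the primary variable and lists the percentage of patients with complications as secondary.
- A reader might infer that a covariate list would clearly add power. That appears in the linear model; under the planned log link the gain over group and hospital alone is not established.

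**Conclusion.** The point holds as a defect in pre-specification with modest consequences. The primary CCI model cannot be reproduced from the plan, and its data-driven part selects on chance. The change is worth making, but the flaw does not invalidate the design or the sample size.

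The size depends on the assumed number and independence of candidates, the variance they explain and equal hospitals of six. The roughly 9% to 14% for wider sets of readings is not a bound, since other cut-offs or candidate sets could give more. The 12 candidates omit blood pressure, heart rate and weight, and weight and BMI are related. The advantage of group and hospital over the rule shrinks as covariates explain more: in the separate linear simulation at 30%, no adjustment and the 0.05 rule are level (0.786 and 0.788). The log-link runs left out hospitals whose CCI values were all zero. Smaller hospitals would produce more of these (0.37² = 0.14 for two patients, 0.37^6 = 0.003 for six), but that concerns the hospital term already in the plan.

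**What to change.** In Sections 1 and 10, delete the sentence on unbalanced characteristics and state that the primary model contains group and hospital only.

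Optionally, add at most about four covariates, recorded before randomization, that the clinical team is confident predict CCI. Name them with their coding before any data split by group are seen, and keep them whatever balance is observed. The documents do not rank predictors, so the choice is clinical; if confidence is lacking, add none.

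Present baseline data descriptively. Label any adjustment for observed imbalance as a sensitivity analysis, with its candidates and cut-off stated. Apply the same fixed model to overall and severe complications, and reconcile the status of overall complications between Sections 1 and 10.

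The cost is wording. Group and hospital alone gains about 0.4 to 2 power points against the rule at 0.05 under the main assumptions. A four-covariate list uses 4 of about 104 residual degrees of freedom (126 − 21 hospitals − 1 for group). If none of the four were prognostic it would lose 0.4 to 1.1 points against the rule, and 1.2 to 2.6 against group and hospital alone.

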Secondary variables:	(1) Total number of postoperative complications per patient; (2) Percent of patients with complications; (3) Total number of stoma related complications per patient; (4) Health-related quality of life; and (5) IPAA functional outcomes (all at 6 months after randomization).
Statistical analysis:	
A Consort Diagram will be used to account for all patients screened for inclusion in the trial; those who were excluded and included and reasons for exclusion; those who were randomized; and those who were followed at each time point or who were lost to follow-up. The primary analysis will be by intention-to-treat, meaning that the patients will be analyzed by the group to which they were randomized. This means that patients randomized to the short interval closure group who have postoperative complications that delay closure will still be analyzed in the group to which they were randomized. Secondary analyses will be done per-protocol (analyzing patients who followed the protocol), and as-treated (analyzing patients by the treatment they actually received).
 
Patient baseline characteristics will be compared between the early and late closure groups using a chi-square test for categorical variables and a t-test for independent samples for normal continuous variables or a Wilcoxon two sample ranks test for non-normal continuous variables.
 
Complications will be reported using the Clavien-Dindo classification. Perioperative details in the two groups will be compared using the same methods as were used for comparing the

Timing of Ileostomy Closure after Ileal Pouch Surgery

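### The zero-inflated Poisson analyses of complication counts name no contrast that compares means, and their model-based tests exceed 5% if the non-zero counts vary more than Poisson

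*Combined protocol and SAP*

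**What the plan says.** Section 10 (Statistical analyses), repeated in Section 1, plans a "comparison of mean number of complications per patient using a zero-inflated Poisson model". It adds that the trial will "compare the mean number of stoma related complications using a zero-inflated Poisson model". In Section 1 the first of these is secondary variable "1) Total number of postoperative complications per patient", and the stoma-related count is variable 3. The share of patients with any complication is a separate variable, "2) Percent of patients with complications".

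The plan does not say whether group enters the count part, the zero part or both, which coefficient or contrast is the test, or whether an overall mean is derived. It names no robust standard error, dispersion check or alternative count model for these outcomes.

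**The concern.** The stated target is a mean count per patient. A zero-inflated Poisson (ZIP) model splits that mean into a share of excess zeros and a Poisson rate among the remaining patients. Its usual output is a group effect on one or both pieces, and the piece usually read off is not the mean. An analyst could choose among tests that answer different questions after seeing the data.

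The Poisson part also forces the variance to equal the mean among patients who are not excess zeros. If a few patients collect many linked events, model-based standard errors are too small. At stake is whether variables 1 and 3, both part of Aim 1, are reported as different when the means are equal, or as similar when the means differ.

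**Working it through.** **The plan's own figure.** The documents size the trial on the CCI only: "10-point difference in their 0 to 100 morbidity scale to be clinically meaningful", "standard deviation of the CCI of 20-22 in two surgical trials", 80% power, alpha 0.05. With n = 2(1.96 + 0.84)²SD²/10², SD 20 gives 63 and SD 22 gives 76 per group. This reproduces "63-76 patients per group, or a total of 126-152 patients". No figure is given for the counts, so 63 and 76 per arm are used below.

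**What the coefficients estimate.** Let π be the excess-zero share and λ the Poisson rate. The mean is (1 − π)λ, so for short (S) versus long (L) interval

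ratio of means = [(1 − π_S)/(1 − π_L)] × (λ_S/λ_L).

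The count coefficient estimates log(λ_S/λ_L). It equals the log ratio of means only if π_S = π_L. Three assumed cases:
- π 0.2, λ 1.5 versus π 0.5, λ 2.4: both means are 1.2, so the mean ratio is 1, but the rate ratio is 2.4/1.5 = 1.6.
- π 0.4, λ 2 versus π 0.6, λ 3: both means are 1.2, but the rate ratio is 3/2 = 1.5.
- π 0.3, λ 2 versus π 0.6, λ 2: the means are 1.4 and 0.8 (ratio 0.57), but the rate ratio is 1.

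**Is π_S = π_L plausible for stoma events?** Section 3 places randomization on day 5 to 12, early closure on day 7 to 12, and late closure no earlier than week 8 (day 56). Complications are counted from randomization. If closure follows the schedule, stoma time after randomization is at most 12 − 5 = 7 days in the early arm and at least 56 − 12 = 44 days in the late arm. Some early patients have almost no time at risk, which acts as an excess zero in that arm only. Shorter exposure could instead act only through λ, so equality is doubtful rather than impossible.

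**Is extra variation plausible?** The Section 5 event list overlaps. Ileostomy stenosis is defined partly through ileostomy dysfunction, which is itself listed. Reoperation and readmission stand beside the events that may cause them. One problem can therefore be counted several times in the same patient.

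**Simulation.** Nominal two-sided 5%, no hospital term. Tests: (a) ZIP count coefficient, group in both parts, Wald; (b) ZIP with group in the count part only, likelihood ratio; (c) overall mean derived from ZIP, model-based error; (d) difference in raw means, empirical variance. There were 3000 replicates for a, c and d, and 300 for b. The Monte Carlo SE is about 0.4 points at 5% for a, c and d, and 1.3 to 2.9 points for b. NB is negative binomial with mean μ and variance/mean 1 + μ/k; for ZIP, variance/mean is 1 + πλ. Percent rejecting at 63 per arm:

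| Scenario (assumed) | a | b | c | d |
|---|---|---|---|---|
| No effect, true ZIP, π 0.4, λ 2 (variance/mean 1.8) | 5.0 | 6.0 | 5.6 | 5.9 |
| No effect, NB μ 1, k 2 (1.5) | 8.5 | 7.3 | 6.1 | 4.9 |
| No effect, NB μ 1.5, k 1 (2.5) | 16.2 | 14.7 | 10.2 | 5.0 |
| No effect, NB μ 2, k 0.5 (5.0) | 29.6 | 31.3 | 15.8 | 5.4 |
| No effect, zero-inflated NB, π 0.3, μ 2, k 1 | 20.1 | 19.7 | 10.7 | 5.0 |
| Equal means, first case above | 63.7 | 29.7 | 4.8 | 5.1 |
| Equal means, second case above | 59.6 | 41.7 | 4.9 | 5.1 |
| Means 1.4 and 0.8, third case above | 4.3 | 20.7 | 63.1 | 66.7 |

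At 76 per arm the picture is the same. NB μ 2, k 0.5 gives a 31.6, c 17.5, d 5.4. The equal-mean cases give a 74.2 and 66.0. The third case gives a 5.0, c 70.6, d 73.4.

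**The log-link models in the fix.** At 76 per arm without site terms, no effect, NB mean 1.3, k 0.7 to 1.5 (400 to 600 trials), the ZIP count term rejected in 16 to 23%, robust Poisson in 5.5 to 6.5% and negative binomial in 6 to 7%. With 152 patients and dummies for 20 assumed sites (500 trials, SE about 1.2 points), negative binomial rejected in 7.2 to 7.4% and robust Poisson in 7.0 to 7.6%.

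**The case against.** The strongest reply is that the plan never says the count coefficient will be the test. A statistician could derive (1 − π)λ in each arm and compare those. That contrast does target the mean: it rejected in about 5% with equal means and had 63 to 71% power in the third case. This stands, so a reader who infers that a ZIP model cannot compare means goes too far. The defect is the unstated contrast. Even the derived mean, however, ran at 6 to 17% under the negative binomial nulls with model-based errors.

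A reader might also infer that any overdispersion produces false positives. It does not. The true ZIP null is overdispersed overall (variance/mean 1.8), and the count coefficient rejected in 4.4 to 5.0%. Inflation needs extra variation among the non-zero counts.

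The documents give no mean count, zero share or dispersion, so the extra variation is inferred from overlapping event definitions, not observed. The equal-mean cases are constructed: effects on zeros and counts cancel exactly. They show what the coefficient measures, not what this trial is likely to see. Finally, the proposed replacement may itself run slightly above 5% with many site dummies.

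**Conclusion.** The concern holds in this form: the plan promises a comparison of means and names a model without the contrast that would deliver it. With group in both parts, neither coefficient is the mean ratio. With group in the count part only, the coefficient is the mean ratio only under equal excess-zero shares, which the difference in stoma time makes doubtful for variable 3.

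If non-zero counts vary more than Poisson, the false-positive rate is about 8.5 to 32% for the count coefficient and 6 to 17% for a derived mean, over negative binomial distributions with mean 1 to 2 and variance/mean 1.5 to 5. Those ranges depend on the assumed dispersion; mild dispersion gives the low end.

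Only secondary variables 1 and 3 are affected. A reader might extend the doubt to the trial's main result, but the documents do not support that. The CCI has its own log-link model, and the sample size rests on the CCI alone. The change is worth making before the data are analyzed.

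**What to change.** In Sections 1 and 10, state that both counts will be compared by the ratio of mean counts per patient (short versus long interval) with 95% CI. Estimate it with a log-link negative binomial or Poisson model with robust standard errors, with arm and adjustment for site. State in advance how small sites are pooled, because separate terms for 17 to 25 centers may push the error rate slightly above 5%. Keep ZIP as a sensitivity analysis, stating where group enters.

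The cost is a sentence or two in each section; no new data or patients are needed. There is some loss of power if the effect lies only in the share of patients with no complication. In one assumed scenario (76 per arm, mean ratio 0.67 acting through zeros), the mean-ratio test had 39% power against 55% for the ZIP zero part. Secondary variable 2 already addresses that question directly.

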7. PHASE 2 (day 7 to 12 or week 8-12): Ileostomy Closure:

- a. Early ileostomy closure will be performed at 7 to 12 days after IPAA.
- b. Late ileostomy closure will be performed 8 - 12 weeks after IPAA.
- c. The ileostomy closure surgical technique is at the discretion of the surgeon.
- d. CRF-5 (ileostomy reversal details) will be completed within 3 days of ileostomy reversal surgery.
- e. Endoscopic examination (optional): Rigid and/or flexible endoscopic examination of the IPAA may be performed per standard practice/standard of care, including non-study-related informed consent, at the discretion of the study surgeon following standard of care. (CRF-5)

8. PHASE 2 (day 7 – 12 to 6 months): Outcome assessment:

- a. The Comprehensive Complication Index and postoperative complications will be assessed and recorded by the study surgeon or trial assistant after review of the medical record, conversation with patient, and members of the care team (when appropriate). This assessment and documentation will begin immediately after randomization is performed and will be updated at 1-2 month intervals until 6 months after randomization. (CRF-6)
- b. Functional outcomes and quality of life (CRF-7): IPAA functional outcomes and quality of life (SF-12) will be assessed and recorded once at 6 months after ostomy reversal.

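### With 0 to 7 scheduled stoma days in the early arm, the zero-inflated Poisson model for stoma-related complications often gives no usable group estimate or Wald interval

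*Combined protocol and SAP*

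**What the plan says.** The Summary (Section 1) lists as its third secondary variable "Total number of stoma related complications per patient", and Aim #1 includes the same count. The Summary and Section 10 give one sentence on its analysis: "We will also compare the mean number of stoma related complications using a zero-inflated Poisson model". Neither place says whether group enters the count part, the inflation part or both, whether hospital is included, which coefficient or test makes the comparison, whether stoma time enters as an offset, or what happens if the fit fails.

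The timing is in Section 3, Overview of time sequence. Item 6 is headed "PHASE 2 (day 5 to 12): RANDOMIZATION". Items 7a and 7b read "Early ileostomy closure will be performed at 7 to 12 days after IPAA" and "Late ileostomy closure will be performed 8 - 12 weeks after IPAA". On recording of complications, item 8a says "This assessment and documentation will begin immediately after randomization is performed". Section 10, on intention-to-treat, keeps delayed closures in the early arm: "patients randomized to the short interval closure group who have postoperative complications that delay closure will still be analyzed in the group".

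**The concern.** A stoma complication needs a stoma. Once randomized, an early-arm patient closed on schedule has one for about a week at most, and a late-arm patient for one and a half to two and a half months. The two arms will therefore supply very unequal amounts of information. The early arm may have no events, and will seldom have a patient with two.

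A zero-inflated Poisson model needs exactly that information. It splits the zeros into patients who cannot have an event and patients who happened to have none, and it does so from the positive counts. Where an arm has almost no positive counts, an arm-specific split is not identified. Where it has none, a log rate ratio is infinite.

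At stake is a named secondary outcome that bears directly on the expected benefit of early closure. The plan promises a comparison of mean numbers, and the model's usual output may not supply one.

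**Working it through.** **1. The plan's own figure.** Section 10 states "our trial would need about 63-76 patients per group, or a total of 126-152 patients". With n per group = 2(1.96 + 0.8416)² × SD² / 10², an SD of 20 gives 62.8, so 63, and an SD of 22 gives 76. The figure reproduces. It concerns the Comprehensive Complication Index; no rate, power or size is stated for stoma complications.

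**2. Scheduled stoma days after randomization (Section 3 windows).**
- Early: closure day 7 to 12 minus randomization day 5 to 12, so 0 to 7 days. With days uniform, and closure not before randomization, the means for randomization days 5 to 12 are 4.5, 3.5, 2.5, 2, 1.5, 1, 0.5 and 0. Their average is 15.5/8 = 1.94.
- Late: day 56 to 84 minus day 5 to 12, so 44 to 79 days; mean 70 − 8.5 = 61.5.
- Ratio: 61.5/1.94, about 32.

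**3. Early-arm events.** Assume a late-arm mean of 0.3 to 1.0 per patient and constant risk per stoma-day. Expected early-arm total = n × late mean × 1.94/61.5. The Poisson chance of no event is exp(−total).

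| n per arm | Late mean | Expected early events | Chance of none |
|---|---|---|---|
| 63 | 0.3 | 0.6 | 55% |
| 63 | 1.0 | 2.0 | 14% |
| 76 | 0.3 | 0.7 | 49% |
| 76 | 1.0 | 2.4 | 9% |

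Simulation with patient frailty (variance 1) gave 9 to 52%.

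**4. Patients with two or more.** With mean m per patient, the chance that nobody in the arm has two is [exp(−m)(1 + m)]^n. For n = 63 this is 0.99 at m = 0.02 and 0.93 at m = 0.05. If each arm has its own inflation term, the early-arm term then runs to its boundary. If the inflation term is common to both arms, the late arm can identify it.

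**5. How often the fit is unusable.** Two kinds of simulation were run: patient frailty with late means 0.3 to 1.0 (unusable: SE above 5 or not computable), and 30 or 50% structural zeros with late means 0.6 or 1.0 (unusable: singular Hessian, any SE of 20 or more, or any absolute coefficient of 15 or more). Runs of about 130 trials per setting carry Monte Carlo error of up to about 9 points.

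| Model form | All in window | 10% delayed to late window |
|---|---|---|
| Group in both parts, frailty | about 90–100% | about 10–80% |
| Group in both parts, structural zeros | 91–96% | 11–52% |
| Group in count part only, frailty | 9–52% | – |
| Group in count part only, structural zeros | 8–37% | 1–12% |

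**6. Whether the difference is detected (frailty simulations).** With 10% delayed, mean early exposure is 0.9 × 1.94 + 0.1 × 61.5 = 7.9 days, so true means differ about 8-fold instead of 32-fold.

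| Test | All in window | 10% delayed |
|---|---|---|
| Wald, count-part coefficient, group in both parts | 40–77% | 36–61% |
| Likelihood ratio, same models | 97–100% | 88–100% |
| Permutation within hospital, difference in means | 94–100% | 84–99% |

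The Wald result has a second cause besides large SEs. With some delayed closures, the early arm looks like many zeros plus a few patients with late-arm counts. The inflation part then absorbs the difference and the count coefficient shrinks. That coefficient answers a different question from the one about mean numbers.

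**The case against.** A reader might infer that the planned analysis will miss the benefit of early closure, and more surely the larger that benefit is. The documents do not support this. They name neither a Wald test nor the count-part coefficient, and likelihood-ratio tests of the same models do about as well as the permutation test. One limit remains: in the structural-zero simulations with 20% delayed, the likelihood-ratio test with group in the count part only fell to 69–92%, while the joint test of group in both parts stayed at 97–100%. Nor does every log-scale model fail when one arm has no events: a Poisson likelihood-ratio test is still defined.

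It can also be said that the mean itself stays estimable. With group in both parts and no other covariates, the fitted mean in each arm, (1 − inflation probability) × Poisson mean, equals the sample mean even at the boundary. That is right. But the plan does not say it will report fitted means, and the usual output is coefficients with Wald intervals.

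Three further cautions stand:
- The start of counting is not wholly consistent. Sections 1 and 3 point to randomization, while Section 10 describes the primary analysis as running to 6 months postoperatively. Counting from IPAA would give 7 to 12 against 56 to 84 days. At the lowest rate the chance of no early event would be exp(−63 × 0.3 × 10.44/61.5) = 4%, where 10.44 = 8.5 + 1.94 is the mean closure day; simulation gave 0 to 5%.
- Section 3 also gives late closure both as 8 to 12 weeks and as at least 8 weeks. These must be reconciled; a longer interval would only widen the exposure gap.
- The documents do not state which events make up the stoma-related count. If closure-site complications are included, both arms are exposed.

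**Conclusion.** The concern holds for the estimate, the interval and Wald inference, not for detection by every version of the model. The 0 to 7 against 44 to 79 days follow from the protocol's own windows and from recording that starts at randomization. Every percentage rests on assumptions that the documents cannot confirm: late-arm means of 0.3 to 1.0, constant risk per stoma-day, the chosen heterogeneity and the share of delayed closures. Delays make unusable fits less frequent but do not make the count coefficient a comparison of means. Hospital was not included in the fitted models; with 17 to 25 centers, or about 5 to 9 randomized patients each (126/25 to 152/17), adding it would make the fit sparser.

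This is more than missing detail, because the model named does not reliably return the quantity promised. It concerns a secondary outcome, and the primary sample size is unaffected.

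**What to change.** In the Summary and Section 10, replace the sentence on stoma-related complications. Make the comparison the difference in mean number per patient by randomized group, counted from randomization, with a p-value from permutation within hospital and a permutation-based interval. A bootstrap interval needs care: an arm with no events resamples to zero every time and contributes no variance. Report stoma-days per arm beside the result.

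If the zero-inflated model is kept, use it only as support. State where group enters, test group by likelihood ratio and report model-based arm means, not Wald tests of the coefficients.

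The cost is SAP wording and a few lines of code, best settled before outcomes are seen by group. The analysis needs no new outcome data. Stoma-days need the closure date, which the closure items in Section 4 do not name, so confirm that Form 5 captures it. The downside is that the result is a difference in means and not a rate ratio. The permutation test is preferred because it always returns a result for the quantity that the plan says it compares, not because it is more powerful than a likelihood-ratio test.
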